9.6.2 Imputation Rules using Multiple Imputation for Sensitivity Analysis

This section describes two methods for multiple imputation of missing data. With each imputation method, the analysis described in **Section 9.6.1** will be repeated using the mITT and PPS.

In addition, for each imputation method, a univariate ANCOVA will be performed at Week 24 which includes the model terms: country/region, treatment group and baseline value.

9.6.2.1 LOCF

The LOCF approach will be applied to the change from baseline in the 3-day average of total awake time in hours per day spent in the OFF state. Intermittent missing data between weeks will not be imputed.

9.6.2.2 Multiple Imputation Method

The sensitivity analysis described in this section is based on a particular assumption of missing not at random (MNAR), or non-ignorable missingness mechanism. For subjects who withdraw from one of the tozadenant treatment groups, the primary endpoint for missing weeks will be derived using multiple imputation based on the mean in the placebo group. Withdrawals from the placebo group will also be imputed based on the placebo data. Intermittent missing data, that is, data that is missing at one week but present at a later week, will be assumed to be missing at random (MAR) and will be imputed using a method appropriate for that assumption. When the missing data has been imputed, the primary endpoint data will be analyzed as a sensitivity analysis using the same method as the primary analysis.

There are two types of missing data that will be imputed:

- 1. Data that is missing at a specific week but present at a later week (intermittent missing data)
- 2. Data that is missing after a subject drops out (monotonic missing data)

The following process will be used to impute all types of missing values for the primary analysis: Step 1:

 For intermittent missing data, Markov Chain Monte Carlo (MCMC) simulation will be used to impute values.

The MCMC imputation process will follow the general pre-planned guidelines described below. However the ability of the process to converge can be dependent on the amount of data that is missing. Convergence of the process will be assessed after unblinding.

The number of burn in iterations will be set at 200, or higher if deemed necessary. The thinning option will be set to select one out of every 100 iterations to insure sufficient separation from previous iterations. Ten imputations will be the initial setting. Trace plots will be checked for

convergence. Factors included in the MCMC algorithm used to impute the missing values will be randomized treatment and the baseline value of the outcome variable.

CONFIDENTIAL

Step 2:

- 3. For monotone missing data, a regression model will be used to impute values as follows:
- 4. Subjects that do not have a Week 2 value or are in the Placebo arm are selected.
- 5. SAS PROC MI will be used to impute missing values using the Baseline time point.
- 6. The imputed data will be combined with the non-missing tozadenant data to achieve a database with data present for all subjects in the analysis set.

Step 3:

7. Step 2 will be repeated for each week iteratively adding a single Week at each step (i.e. the second imputation will have Baseline, Week 2 in the model, the next will also include Week 6).

Step 4:

8. The final outcome dataset (which will have no missing data) will be analyzed using the primary MMRM analysis.

Estimates will be derived using the SAS PROC MIANALYZE procedure.

Because intermittent missing values may not occur, and there may not be patients in the combined tozadenant dose group dropping out at a designated week, not all the steps above will necessarily be implemented. Assuming there will be subjects in some of the tozadenant groups dropping out from the study, the total number of imputations will be set at 10 if there are intermittent missing values, and 20 otherwise.

The total number of imputations is controlled as follows. Set K = 10 if there are intermittent missing values, and K = 20 otherwise. Starting from Step 2, select the week where the combined tozadenant group had the maximum total number of dropouts among all weeks. Only at this week will the number of imputations be set to K using the regression method at that step. If more than one week has the same maximum number of tozadenant dropouts, then the earliest among such weeks will be selected to have K imputations. Only one imputation will be made for all other weeks.

The seed used for the primary side for Step 1 will be 32192. All subsequent seeds generated will be stored for reproduction of the results if necessary.

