3.1.2 Planned Number of Patients and Sites

Part A: Approximately 645 patients will be screened, assuming a 30% screen failure rate, to randomize 450 patients.

Part B: It is anticipated that 80% of the randomized patients (i.e., approximately 360 patients) will complete Part A and continue into the open-label phase.

Approximately 80 sites will participate in the study.

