3.2 Sample Size Considerations

The primary efficacy endpoint is the change from Baseline to Week 24 in the number of hours per day spent in the OFF state. A sample size of 150 in each group will provide 85% power to detect a difference in mean response of 0.9 hours between tozadenant and placebo assuming the common SD is 2.6 hours and using a two group t-test with a 0.050 two-sided significance level. Across the 3 treatment groups, the total number of patients to be randomized is 450.

Although the sample size calculation is based on the primary endpoint, OFF time, for this study the total sample size of 450 patients is anticipated to yield power to detect treatment differences

in the two key secondary endpoints as summarized in the table below. The assumed treatment differences and standard deviations are based on the findings of the SYN115-CL02 study.

CONFIDENTIAL

Estimated Power for Key Secondary Efficacy Endpoints

Secondary Endpoint	SYN11	Power	
120 mg BID vs. placebo	Treatment	Standard	
	Difference	Deviation	
Good ON time: Number of hours spent in the	1.19	2.64	97%
ON state without troublesome dyskinesia			
UPDRS Parts II + III total score	3.00	8.38	87%

Approximately 645 patients will be screened, assuming a 30% screen failure rate, to randomize 450 patients.

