3.3 Randomization

During Part A, an IXRS will be used for assigning eligible patients to a treatment regimen based on a predetermined randomization schedule. The final randomization schedule will be created and sent to the IXRS provider. The IXRS is responsible for assigning blinded IMP kits to randomized patients, as appropriate, according to the randomization and the visit schedule. Patients will be randomly allocated in equal proportion (1:1:1) to 1 of 3 double-blind treatment groups:

- Group A: tozadenant 60 mg BID (one 60 mg active tozadenant tablet plus one placebo tablet, BID)
- Group B: tozadenant 120 mg BID (two 60 mg active tozadenant tablets, BID)
- Group C: placebo BID (two placebo tablets, BID)

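### The placebo-based imputation draws K times at one week only, so its between-imputation variance can be too small when no intermittent gaps exist and that week is late; the stated number of imputations is also inconsistent

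*SAP*

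**What the plan says.** SAP 9.6.2.2 describes a missing-not-at-random sensitivity analysis in which patients who withdraw are imputed from the placebo group.

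- **Step 1** fills intermittent gaps by MCMC: "Ten imputations will be the initial setting".
- **Steps 2 and 3** fill monotone dropout by regression, one week at a time, each week conditioning on the completed earlier weeks.
- **Number of draws.** K is 10 if intermittent gaps exist and 20 if not. The plan picks the week with most dropouts in the combined tozadenant group, ties going to the earliest: "Only at this week will the number of imputations be set to K using the regression method at that step". For the rest, "Only one imputation will be made for all other weeks".
- **Total.** The section also says that "the total number of imputations will be set at 10 if there are intermittent missing values", and 20 otherwise.
- **Pooling** is by PROC MIANALYZE.

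SAP 9.6.2 applies this to the mITT and the PPS, and SAP 9.6.3 extends it to both key secondary endpoints.

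**The concern.** Standard pooling treats the K completed datasets as independent completions. Their spread, the between-imputation variance B, is meant to carry all the uncertainty due to missing data. In a sequential scheme that branches into K datasets only at the peak week, every earlier week has been filled once and that fill-in is common to all K. Uncertainty from those weeks cannot enter B. How much is lost depends on which week happens to have most dropouts.

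This is the plan's only analysis built on a stated missing-not-at-random assumption, so its standard error should be the one that the pooling rule assumes. The count matters too. If ten MCMC datasets each receive K = 10 draws at the peak week, there are 100 nested datasets and not 10, so two programmers could run different analyses from the same text.

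**Working it through.** **Scale, and the plan's own figure.** SAP 3.2 states: "A sample size of 150 in each group will provide 85% power to detect a difference in mean response of 0.9 hours", with "common SD is 2.6 hours and using a two group t-test with a 0.050 two-sided significance level". The SE of a difference is 2.6 × √(2/150) = 0.300 h. Then 0.9/0.300 − 1.96 = 1.04 and Φ(1.04) = 0.850, so the stated 85% is reproduced (noncentral t: 0.848). The plan gives no figure for B, so its size was simulated.

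**Inputs from the documents.**
- 150 per arm; "Patients will be randomly allocated in equal proportion (1:1:1) to 1 of 3 double-blind treatment groups" (SAP 3.3).
- About 20% not completing: "It is anticipated that 80% of the randomized patients (i.e., approximately 360 patients) will complete Part A" (Protocol 3.1.2).
- K = 20 without gaps; 10 MCMC datasets and K = 10 with gaps.
- The mITT requires a usable diary from at least one visit after baseline (SAP 3.1.3). A dropout with no Week 2 diary is therefore outside it, and the first monotone imputation of OFF time is at Week 6.
- The PPS requires Week 24 OFF time (SAP 3.1.4), so it has no monotone OFF-time dropout and the K rule has nothing to act on.

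**Assumptions not in the documents.** The split of 30 dropouts per arm over weeks; visit correlation (exchangeable 0.5, exchangeable 0.7 or AR(1) 0.85, each scaled to a change SD of 2.6 h); no treatment effect; two arms; no country term; a Week 24 ANCOVA in place of the MMRM. One imputation was read as one draw per existing dataset. There were 300 trials per scenario.

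**Comparison without gaps.** The SAP rule was set against 20 datasets started at the first imputed week with one draw per dataset at each later week. Entries are SAP rule divided by reference.

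| Peak week (newly missing per arm at 6/12/18/24) | B, exch. 0.5 | B, exch. 0.7 | B, AR(1) 0.85 | SE, range |
|---|---|---|---|---|
| 6 (12/6/6/6) | 0.943 | 1.013 | 1.023 | 0.995-1.002 |
| 12 (6/12/6/6) | 0.969 | 0.927 | 0.972 | 0.994-0.998 |
| 18 (6/6/12/6) | 0.971 | 0.951 | 0.849 | 0.991-0.998 |
| 24 (6/6/6/12) | 0.928 | 0.913 | 0.578 | 0.975-0.994 |
| 24 (14/0/0/16) | 0.926 | 0.893 | 0.597 | 0.977-0.994 |

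In the first row the two schemes are identical, so 0.94-1.02 shows the simulation noise. The smallest shortfalls at Weeks 12 and 18 lie within it; the AR(1) values at Weeks 18 and 24 do not.

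**Why the SE moves so little.** Total variance is T = W + (1 + 1/K)B, where W is the average within-imputation variance, and B was only 11-15% of T. In the worst case B/T = 0.108 and B is cut by 1 − 0.578 = 0.422. The SE ratio is then √(1 − 1.05 × 0.108 × 0.422) = √0.952 = 0.976, against 0.975 simulated. On the plan's scale, 2.5% of 0.300 h is 0.0075 h, about half a minute.

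**With gaps (ten MCMC datasets, K = 10 in each).** The earlier weeks now have ten separate draws. The B ratio was 0.97-1.03 and the SE ratio 0.995-1.000.

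**Pooling 100 nested datasets as if independent.** Let b be the between-nest variance and w the within-nest variance. The expected sums of squares are 10 × 9 × (b + w/10) = 90b + 9w between nests and 10 × 9 × w = 90w within nests. Dividing the total by 99 gives (90/99)b + w, so the between-nest part is multiplied by 0.91.

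**Type I error.** Null rejection was 0.7-4.7% under every scheme, and the pooled variance was 1.1-1.6 times the empirical variance.

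**The case against.** The strongest case for leaving the text alone is that nothing of consequence follows. The shortfall needs two conditions together: no intermittent gap anywhere, and a late peak. With about 450 patients and five diary visits, at least one gap is likely, and the MCMC branch then nearly repairs the problem. The selection rule is fixed in advance with a tie-break, so it gives the analyst no freedom. B depends on the dropout pattern under complete chains as well. The worst SE change is about half a minute of OFF time against a 0.9 h target, and the pooled variance remained conservative.

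All of that stands, and it limits the point to a minor one. It does not defend the rule, which has no statistical benefit over complete chains with the same number of datasets. Nor does it settle the count: in the branch most likely to be used, the text supports either ten chains or 100 nested datasets.

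A reader might infer that B is always too small. It is not when the peak is the first imputed week, nor materially so when gaps exist. A reader might also take the single imputation at weeks after the peak to be shared by all datasets, which would make B zero at Week 24 for any earlier peak. The text does not exclude that. But each later week conditions on completed weeks that already differ between datasets, so one draw per dataset is the natural reading.

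**Conclusion.** The rule is wrong as written, with a small effect. Without intermittent gaps and with a peak after the first imputed week, B is too small by roughly 3-15% for a peak at Weeks 12-18 and 7-42% at Week 24. The range reflects visit correlation and dropout timing that had to be assumed. The SE is at most about 2.5% too small. There is no loss when the peak comes first (Week 6 for OFF time in the mITT), and PPS OFF time is unaffected. With gaps, the shortfall almost disappears and the live defect is the conflict between 10 and 100 imputations.

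A reader might conclude that the sensitivity analysis becomes anticonservative or that the primary result is at risk. Neither is supported: no type I error inflation was seen, and the effect is confined to the missing-not-at-random sensitivity analysis of the primary and key secondary endpoints. The sizes rest on a simplified simulation with a few percent of noise in the B ratios.

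**What to change.** Delete the rule that selects one week and sets K there. State one number M of complete chains, at least the planned 20; a larger M is a matter of preference. Each chain has its own MCMC fill-in where gaps exist, so the Step 1 setting rises from ten to M, and its own regression draw at every week from the first imputed week onward. Say explicitly that each week uses one draw per dataset. Pool the M results with PROC MIANALYZE. This also removes the conflict over the total, because each MCMC dataset then feeds exactly one chain.

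The computing cost is trivial and the code becomes simpler. The real cost is a documented SAP revision before unblinding, which matters because the SAP supports a Special Protocol Assessment. The SAP was written against protocol Amendment 1 and the protocol is now at Amendment 3, so the change can go into the same update.

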9.6.3 Key Secondary Variables

All secondary variables will be analyzed by the same model as described for the primary outcome variable, with the baseline covariate value being the baseline outcome variable of interest included in the statistical model instead of the baseline number of hours of OFF time in the mITT and PPS. The sensitivity analyses described in **Section 9.6.2** will also be performed for the key secondary outcomes.

The following key secondary efficacy endpoints will be summarized and analyzed:

- Change from baseline to Week 24 in the number of hours per day spent in good ON time, defined as the sum of ON time without dyskinesia and ON time with non-troublesome dyskinesia.
- Change from baseline to Week 24 in UPDRS Parts II (ADL subscale) + III (motor subscale) total scores.

For the UPDRS Part I, II, III, sum of Parts II+III and I – III and Part IV (Part A, B and C and total) if a question making up the total score is missing, the total score for that Part will not be determined for the subject for the given visit, as well as the sum of Parts I - III. Subjects with missing total score will be footnoted.

CONFIDENTIAL

9.6.4 Other Secondary Variables

All other secondary variables will be analyzed by the same model as described for the primary outcome variable, with the covariate value being the baseline outcome variable of interest included in the statistical model instead of the baseline number of hours of OFF time. The analyses will only be done in the mITT. No sensitivity analyses are planned and there will be no adjustment for multiplicity.

The following other secondary efficacy variables to be summarized and analyzed include: the change from Baseline to Week 24 (where applicable) for the following:

- 1. CGI-I at Week 24
- 2. PGI-I at Week 24.
- 3. UPDRS Part III (motor subscale) score in the ON state.
- 4. CGI-S.
- 5. UPDRS Part II (ADL subscale) score.
- 6. Number of hours per day spent in the ON state (without dyskinesia, with non-troublesome dyskinesia, or with troublesome dyskinesia).
- 7. Number of hours per day spent in the ON state without dyskinesia.
- 8. Number of hours per day spent in the ON state with any dyskinesia (troublesome or non-troublesome).
- 9. Number of hours per day spent in the ON state with non-troublesome dyskinesia.
- 10. PD-related quality of life as measured by PDQ-39 (total score and individual domain scores).
- 11. UPDRS Part IV score.
- 12. UPDRS Part I score.

For the UPDRS Part I, II, III, sum of Parts I – III and Part IV (Part A, B and C and total) if a question making up the total score is missing, the total score for that Part will not be determined for the subject for the given visit, as well as the sum of Parts I - III. Subjects with missing total score will be footnoted.

For the PDQ-39 questionnaire, if a question is not answered, then the total score or the dimension score for the PDQ-39 will not be determined for the subject at the visit. Missing data will be footnoted.

Dimensions for the PDQ-39 will be derived by the sum of scores of each question in the dimension divided by (maximum score per question multiplied by number of questions in the dimension). The PDQ-39 single index score of the 8 dimensions will be derived as the sum of all 8 dimension scores divided by 8. The mobility dimension consists of questions 1 to 10 of the PDQ-39, activities of daily living dimension consists of questions 11 to 16, emotional well-being dimension consists of questions 17 to 22, stigma dimension consists of questions 23 to 26, social support dimension consists of questions 27 to 29, cognitive impairment dimension consists of questions 30 to 33, communication dimension consists of questions 34 to 36 and bodily discomfort dimension consists of questions 37 to 39.

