Table 1: Part A – Schedule of Events/Evaluations (continued)

	Study Period	Screening a	Baseline Predose		Doubl	e-Blind Tr (24 weeks			Early Termination ^x	Safety Follow-Up for ET	Unscheduled
	Study Week	-6 to -1	BL	2 (±3 d)	6 (±3 d)	12 (±3 d)	18 (±3 d)	24 (±7 d)	Termination	28 (±3) d after last dose of IMP	Cuscucuucu
Assessments	Study Visit	V1	V2	V3	V4	V5	V6	V7	A98	A99	A97
PD diary review		X	X	X	X	X	X	X	X ^j		
Final verification o exclusion criteria	f inclusion and		X								
Patient randomizati	on		X								
CGI-I k				X	X	X	X	X	X ^x		
PGI-I ^k				X	X	X	X	X	X ^x		
CGI-S k			X	X	X	X	X	X	X ^x		
SCOPA-cog k			X					X	X		
PDQ-39 k			X			X	X	X	X		
EQ-5D-5L ^k			X					X	X		
TSQM-9 k					X			X	X		
Sudden onset of sle	ер		X	X	X	X	X	X	X	X	
ESS k			X	X	X	X	X	X	X	X	
Fall questionnaire			X					X	X		
Healthcare Resource				X	X	X	X	X	X		
IMP dispensing and	l return ¹		X	X	X	X	X	X	X		X
Recording of AEs		X m	X m	X	X	X	X	X	X	X	X
Anti-PD medication				Patient	s continue	stable dose	of levodop	a and other a	llowed anti-PD medic	cations throughout Part	Α.
FSH test, females v postmenopausal for		X									
Thyroperoxidase ar	ntibody	X									
Laboratory tests: he chemistry o (includi		X	X	X	X	X	X	X	X	X	X ^d
Urine pregnancy te childbearing potent		X	X	X	X	X	X	X	X	X	X ^d
Urinalysis r		X	X	X	X	X	X	X	X	X	X ^d
Tozadenant blood s			X	X ^t	X	X	X	X ^t	X ^t		X ^d
Pramipexole blood (applicable patients			X ^u	X v	X	X	X	X v	X v		X w
eCRF completion	•	X	X	X	X	X	X	X	X	X	X

Confidential Page 34 of 195

Table 1: Part A – Schedule of Events/Evaluations (continued)

TOZ-CL05 PART A: DOUBLE-BLIND PHASE

AE, adverse event; BP, blood pressure; CGI-I, Clinical Global Impression of Improvement; CGI-S, Clinician Global Impression of Severity; C-SSRS, Columbia-Suicide Severity Rating Scale; d, day(s); ECG, electrocardiogram; eCRF, electronic case report form; EQ-5D-5L, EuroQol 5D-5L Health Questionnaire; ESS, Epworth Sleepiness Scale; ET, Early Termination; FSH, follicle stimulating hormone; IMP, investigational medicinal product; mMIDI, Modified Minnesota Impulse Disorders Interview; MMSE-II, Mini-Mental State Exam—Second Edition (MMSE-II); P, pulse (beats per minute); PD, Parkinson's disease; PDQ-39, Parkinson's Disease Quality of Life Questionnaire; PGI-I, Patient Global Impression of Improvement; SCOPA-cog, Scales for Outcomes in Parkinson's Disease - cognition; TSQM-9, Treatment Satisfaction Questionnaire for Medication; UPDRS, Unified Parkinson's Disease Rating Scale; V, Visit.

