7.3 Clinical/Patient Global Impression Scales (CGI-S, CGI-I and PGI-I)

Clinical Global Impression of Severity (CGI-S):

For the CGI-S, the investigator or rater is asked, considering his or her total clinical experience with the PD population, to rate the severity of the patient's disease at that time, based on a 1-7 point weighted scale ranging from "normal, not at all ill" (1) to "among the most extremely ill patients" (7). A zero score is assigned if the score is not assessed.

Clinical Global Impression of Improvement (CGI-I):

For the CGI-I, the investigator or rater is asked to rate the patient's total improvement, whether or not in his or her judgment it is due entirely to drug treatment, based on a 1-7 point weighted

scale ranging from "very much improved" (1) to "very much worse" (7). A zero score is assigned if the score is not assessed.

Patient Global Impression of Improvement (PGI-I):

For the PGI-I, the patient is asked to rate the total improvement of their PD, whether or not in the patient's judgment it is due entirely to drug treatment, based on a 1-7 point weighted scale ranging from "very much improved" (1) to "very much worse" (7). A zero score is assigned if the score is not assessed.

Examples of the CGI-S, CGI-I, and PGI-I scales are provided in **Appendix 15.4**.

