11.4.4 Other Secondary Efficacy Analyses

The other secondary efficacy analyses include the change from Baseline to Week 24 (where applicable), for the following:

- 1. CGI-I.
- 2. PGI-I.
- 3. UPDRS Part III (motor subscale) score in the ON state.
- 4. Investigator global impressions of severity of illness (CGI-S).
- 5. UPDRS Part II (ADL subscale) score.
- 6. Number of hours per day spent in the ON state (without dyskinesia, with non-troublesome dyskinesia, or with troublesome dyskinesia).
- 7. Number of hours per day spent in the ON state without dyskinesia.
- 8. Number of hours per day spent in the ON state with any dyskinesia (troublesome or non-troublesome).
- 9. Number of hours per day spent in the ON state with non-troublesome dyskinesia.
- 10. PDQ-39 (total score and individual domain scores).
- 11. UPDRS Part IV.
- 12. UPDRS Part I.

All continuous other secondary efficacy variables will be analyzed using the model defined in the primary analysis of OFF time (Section 11.4.1) and the mITT. Sensitivity analyses of the other secondary efficacy variables are not planned.

All other variables will be analyzed using adequate statistical methods.

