15.4 Clinical/Patient Global Impression Scales (CGI-S, CGI-I and PGI-I)

Clinical Global Impression of Improvement (CGI-I)

Rate total improvement whether or not in your judgment it is due e	ntirely to drug treatment.
Compared to his/her condition at admission to the study, how much	n has he/she changed?

1 = Very much improved
2 = Much improved
3 = Minimally improved
4 = No change
$\int 5 = Minimally worse$
6 = Much worse
$\boxed{}$ 7 = Very much worse

Clinical Global Impression of Severity (CGI-S)

Tozadenant

Considering your total clinical experience with this particular population, how severe is the subject's Parkinson's disease at this time?
1 = Normal, not at all ill
2 = Borderline ill
4 = Moderately ill
5 = Markedly ill
6 = Severely ill
7 = Among the most extremely ill patients

Patient Global Impression of Improvement (PGI-I)

Rate total improvement of your Parkinson's disease, whether or not in your judgment it is due entirely to drug treatment. Compared to your condition at admission to the study, how much have you changed? Place an X in one of the boxes below best describing your impression.

1. Very much improved.
2. Much improved.
3. Minimally improved.
4. No change.
5. Minimally worse.
6. Much worse.
7. Very much worse.

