4.5 Predetermined Covariates and Prognostic Factors

The primary, secondary and exploratory analyses will be based on a mixed model repeated measures (MMRM) ANCOVA, where the covariate in the analysis is the baseline value of the respective response variable. For example, if the number of hours per day spent in the OFF state is being analyzed, the covariate will be the baseline number of hours per day spent in the OFF state. More details are provided in **Sections 9.6.1** to **9.6.3** of this SAP.

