5.7 Baseline Non-Blood Pressure, Non-Pulse Rate and Non-Diary Data

Baseline is defined as the last measurement prior to first dose of study medication at study Day 1. If for any parameter the study Day 1 pre-dose value is not done or missing, then the last value obtained at a Screening visit is used as Baseline.

CONFIDENTIAL

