8 UNBLINDING UPON COMPLETION OF PART A

Immediately after Part A (double-blind phase) of the study completes and the database is cleaned and locked, the responsible CRO(s) will follow their SOPs to unblind the Part A. . A blinded data review will be performed (per ICH E9) before the database is locked and before the study groups are unblinded. Primary and secondary efficacy analyses are final and will not be modified. Exploratory analyses that do not involve the primary or secondary efficacy analyses are subject to modification.

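### SAP 9.6.4 gives CGI-I and PGI-I a baseline covariate that cannot exist, and its PDQ-39 missing-item rule drops two scores for patients without a partner

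*SAP*

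**What the plan says.** SAP 9.6.4 lists twelve other secondary variables, CGI-I and PGI-I at the top, and sends all of them to the MMRM of SAP 9.6.1, "with the covariate value being the baseline outcome variable of interest included in the statistical model". SAP 4.5 states the same as a general rule, "where the covariate in the analysis is the baseline value of the respective response variable". Neither section makes an exception. Where a Day 1 pre-dose value is missing, SAP 5.7 provides that "then the last value obtained at a Screening visit is used as Baseline".

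Protocol 11.4.4 is narrower. It applies the primary model to the continuous other secondary variables and says of the rest: "All other variables will be analyzed using adequate statistical methods". It does not say to which class the two global scales belong.

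For the PDQ-39, SAP 9.6.4 leaves the total or dimension score undetermined at a visit when a question has no answer. It builds social support from questions 27 to 29 and the single index from all eight dimensions.

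SAP 8 closes the matter: "Primary and secondary efficacy analyses are final and will not be modified".

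**The concern.** An improvement scale has no value before there is anything to compare. If the SAP requires each outcome's own baseline, the stated analysis of the first two other secondary endpoints cannot be run, and someone must drop or replace the covariate later. That choice should be made while the data are blinded.

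The PDQ-39 rule treats an item that does not apply as if it had been skipped. Question 28, about support from a spouse or partner, offers a box for patients who have neither. If that box voids the score, social support and the index describe only patients with a partner, a restriction the plan never states as intended.

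**Working it through.** The plan gives no figure of its own on this point, so the check sets the passages side by side and then counts.

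**1. Is there a baseline for CGI-I and PGI-I?**
- Protocol Table 1 and SAP Table 3-1: both rows are empty at Screening and Baseline and start at Week 2. The CGI-S row is marked at Baseline.
- Protocol 6.2.2.1 (Screening) and 6.2.3.3 (Baseline): neither scale is listed. CGI-S is listed at Baseline.
- Protocol Appendix 15.4: the PGI-I asks "Compared to your condition at admission to the study, how much have you changed", and the CGI-I asks the clinician the same. No pre-treatment value is possible.
- The Screening fallback in SAP 5.7 therefore finds nothing.

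**2. Can the model be fitted?** Take 450 patients, 150 in each of 3 groups, before dropout.
- Own baseline as covariate: missing for everyone, so 0 complete records.
- Without that covariate: all 450 patients are usable.
- Baseline CGI-S as covariate, 5 weeks, two regions assumed: intercept 1 + group 2 + week 4 + group-by-week 8 + region 1 + covariate 1 = 17 columns. The design matrix has rank 17 of 17, so the model is estimable.

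**3. The zero code.** Protocol 7.3 scores all three global scales from 1 to 7, with 1 the most favourable, and adds "A zero score is assigned if the score is not assessed". The SAP does not set this code to missing. Left as a number, an unassessed visit would rank better than the best possible rating, and an unassessed baseline CGI-S would corrupt the replacement covariate.

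**4. PDQ-39 scoring with the question 28 box ticked.** SAP 9.6.4 divides the sum of the item scores by the maximum item score times the number of questions. Suppose the other 38 items are all scored 2 on an assumed 0-4 coding.
- Under the SAP rule, social support is undetermined, so the index is too. Lost: 2 of 9 scores (8 dimensions + index). The other seven dimensions are 0.50 each.
- With questions 27 and 29 only: (2 + 2)/(4 × 2) = 0.50, and the index is (7 × 0.50 + 0.50)/8 = 0.50.
- If the tick were instead counted as zero over three items: (2 + 0 + 2)/(4 × 3) = 0.33, and the index would be (3.50 + 0.33)/8 = 0.48. How the box is treated changes the score.

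**5. Visits lost.** The PDQ-39 is scheduled at Baseline and Weeks 12, 18 and 24, and not at Screening. A tick at one follow-up visit loses that visit. A tick at Baseline removes the covariate and, under SAP 5.8, the change score, so 3 of 3 scheduled follow-up visits are lost for both scores.

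**6. Size.** The share without a partner is not in the documents; 10-30% is an assumption.
- Of 450 randomized: 450 × 0.10 = 45 to 450 × 0.30 = 135.
- Of the 360 expected to complete Part A (protocol 3.1.2): 36 to 108.
- Per group, if the share is even across groups: 150 × 0.90 = 135 down to 150 × 0.70 = 105.
- Standard error ratio, with equal variance: 1/√0.90 = 1.054 to 1/√0.70 = 1.195.

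**The case against.** The CGI-I and PGI-I gap reveals itself: the first program run returns no records, so no wrong estimate can pass unnoticed, and dropping the term cures it. The SAP limits the change from Baseline to endpoints where it applies, so the Week 24 score is correctly defined. That is true of the response. The covariate sentence carries no such limit.

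Baseline CGI-S is also not the only candidate. Protocol 11.4.4 points to the OFF-time model, whose covariate is baseline OFF hours, and every mITT patient has valid baseline diaries by definition. This is fair: baseline OFF hours or no covariate would also run, and estimability alone does not make CGI-S the better choice. The case for CGI-S is that it is a global PD rating taken at Visit 2. What matters most is that one choice is written down before unblinding.

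On the PDQ-39, a ticked box might count as an answer, since the form asks for one box per question. Even so, the SAP gives the tick no score, and a three-item formula cannot be completed with two scored items. A rule is missing on either reading.

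Finally, the partner share is assumed, the even-spread calculation shows lost precision rather than bias, and the SAP still has open placeholders, so another revision would be ordinary. All of this stands. It limits the weight of the point but does not remove the defect.

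**Conclusion.** Both parts hold. The stated model for CGI-I and PGI-I cannot be fitted, because no patient has the covariate at Baseline or Screening; only the covariate rule is at fault. The PDQ-39 rule removes social support and the single index for any patient who ticks the no-partner box, for the whole of follow-up if the tick is at Baseline.

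The reach is limited. These are other secondary endpoints with nominal p-values outside the fixed sequence, and the primary and key secondary tests are untouched. The patient counts and the 5-20% loss of precision rest on the assumed 10-30% share, spread evenly over groups; the defect itself does not depend on that share. The text should be corrected before unblinding, since SAP 8 allows no later change.

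**What to change.** - In SAP 9.6.4 and 4.5, exempt CGI-I and PGI-I from the own-baseline rule. Fit the same MMRM to the observed scores, take the Week 24 contrast, and use CGI-S from Visit 2 as the covariate for both.
- Set the zero code of protocol 7.3 to missing in these scores and in the CGI-S covariate.
- In SAP 9.6.4, when the question 28 box is ticked, score social support at that visit from questions 27 and 29 with a two-item denominator, then compute the index as planned.

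The cost is a short insertion in SAP 9.6.4 and one exception in 4.5; all inputs are already collected. There are two drawbacks: social support rests on two items for these patients, and a clinician-rated covariate may gain less precision for the patient-rated PGI-I.
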